5.5 Intensification I – AE

The following Intensification I therapy guidelines are for low risk patients and for patients with high risk disease who do not have an appropriate donor for SCT. Intensification I will last for 28 days or longer. It is suggested, but not required, that patients have an ANC > 1,000/ μ L and a platelet count > 75,000/ μ L before proceeding with Intensification I therapy.

Intrathecal Cytarabine (IT ARAC): IT

IT ARAC may be administered on Day 1 of Intensification I or with the bone marrow evaluation at the end of Induction II.

Age-based dosing:

Age (yrs)	Dose
------------------	-------------

0 - 0.99	20 mg
1 - 1.99	30 mg
2 - 2.99	50 mg
≥ 3	70 mg

High Dose Cytarabine (HD ARAC): IV over 1 - 3 hours

Days: 1 through 5.

Dose: 1000 mg/m²/dose, every 12 hours, (i.e., 2000 mg/m²/day, divided BID), or 33 mg/kg/dose, every 12 hours (i.e., 66 mg/kg/day, divided BID) if BSA < 0.6 m².

Suggested premedications and supportive care: Administer steroid eye drops (0.1% dexamethasone or 1% prednisolone ophthalmic solution), 2 drops to each eye every 6 hours, beginning immediately before the first dose and continuing for 24 hours after the last dose. If patient does not tolerate steroid eye drops, may administer artificial tears on an every 2-4 hour schedule. Patients in whom serum creatinine is > 2 mg/dL or > 2 x normal for age, must have a CrCl performed (Day 1) and doses of cytarabine adjusted as outlined.

Etoposide (ETOP): IV over 60 - 120 minutes

Days: 1 through 5.

Dose: 150 mg/m²/dose, or 5 mg/kg/dose if BSA < 0.6 m².

Note: Slow rate of administration if hypotension occurs. The use of an in-line filter during the infusion is suggested. Each dose of etoposide should immediately follow the 1st, 3rd, 5th, 7th and 9th doses of cytarabine.

5.6 Intensification I for FLT3-ITD patients – AE with sorafenib

The following Intensification I therapy guidelines are for patients with FLT3-ITD AML who do not have an appropriate donor for SCT. Intensification I will last for 28 days or longer. It is suggested, but not required, that patients have an ANC > 1,000/µL and a platelet count > 75,000/µL before proceeding with Intensification I therapy.

Intrathecal Cytarabine (IT ARAC): IT

IT ARAC may be administered on Day 1 of Intensification I or with the bone marrow evaluation at the end of Induction II.

Age-based dosing:

Age (yrs)	Dose
0 - 0.99	20 mg
1 - 1.99	30 mg
2 - 2.99	50 mg
≥ 3	70 mg

High Dose Cytarabine (HD ARAC): IV over 1 - 3 hours

Days: 1 through 5.

Dose: 1000 mg/m²/dose, every 12 hours, (i.e., 2000 mg/m²/day, divided BID), or 33 mg/kg/dose, every 12 hours (i.e., 66 mg/kg/day, divided BID) if BSA < 0.6 m².

Suggested premedications and supportive care: Administer steroid eye drops (0.1% dexamethasone or 1% prednisolone ophthalmic solution), 2 drops to each eye every 6 hours, beginning immediately before the first dose and continuing for 24 hours after the last dose. If patient does not tolerate steroid eye drops, may administer artificial tears on an every 2-4 hour schedule. Patients in whom serum creatinine is > 2 mg/dL or > 2 x normal for age, must have a CrCl performed (Day 1) and doses of cytarabine adjusted as outlined.

Etoposide (ETOP): IV over 60 - 120 minutes

Days: 1 through 5.

Dose: 150 mg/m²/dose, or

5 mg/kg/dose if BSA < 0.6 m².

Note: Slow rate of administration if hypotension occurs. The use of an in-line filter during the infusion is suggested. Each dose of etoposide should immediately follow the 1st, 3rd, 5th, 7th and 9th doses of cytarabine.

Sorafenib (SORAF): PO

Days: 6 through 33

Dose: 200 mg/m²/dose daily, rounded to accommodate tablet size. The maximum dose will be 400 mg.

Dose to be administered per dosing nomogram in Appendix I.

Note: Sorafenib tablets should be taken at least 1 hour before or 2 hours after food. Tablets should be taken with clear liquids (approximately 2 to 4 ounces for children < 12 years and 4 to 8 ounces for ≥ 12 years). If taken with food, sorafenib should be taken with a moderate to low fat meal. Tablets should not be crushed and should be swallowed whole. However, sorafenib tablets can be dispersed in water to facilitate the administration to subjects that cannot swallow tablets.

5.7 Intensification II – HD ARAC/LASP

The following Intensification II therapy guidelines are for low risk patients and for patients with high risk disease who do not have an appropriate donor for SCT. Intensification II lasts 28 days or longer.

It is suggested, but not required, that patients have an ANC $> 1,000/\mu\text{L}$ and a platelet count $> 75,000/\mu\text{L}$ before proceeding with therapy.

High Dose Cytarabine (HD ARAC): IV over 3 hours

Days: 1, 2 and 8, 9

Dose: 3,000 mg/m²/dose, every 12 hours (i.e., 6,000 mg/m²/day, divided BID), or

100 mg/kg/dose, every 12 hours (i.e., 200 mg/kg/day, divided BID) if BSA < 0.6 m².

Suggested premedications and supportive care: Administer steroid eye drops (0.1% dexamethasone or 1% prednisolone ophthalmic solution), 2 drops to each eye every 6 hours, beginning immediately before the first dose and continuing for 24 hours after the last dose. If patient does not tolerate steroid eye drops, may administer artificial tears on an every 2-4 hour schedule. Patients in whom serum creatinine is > 2 mg/dL or > 2 x normal for age, must have a CrCl performed (Days 1 and 8) and doses of cytarabine adjusted as outlined.

Erwinia L-asparaginase (Erwinaze): IM (may be given IV over 1 hour)

Days: 2, 9 (one dose per day, 2 doses total for the entire course)

Dose: 25,000 IU/m² (830 IU/kg/dose if BSA < 0.6 m²)

Note: Erwinia asparaginase should be given 6 hours after the start of cytarabine doses 4 and 8. If Erwinia asparaginase is not available, pegaspargase should not be given. Rather, asparaginase should be omitted.

5.8 Intensification II for FLT3-ITD patients – HD ARAC/LASP with sorafenib

The following Intensification II therapy guidelines are for patients with FLT3-ITD AML who do not have an appropriate donor for SCT. Intensification II lasts 28 days or longer.

It is suggested, but not required, that patients have an ANC > 1,000/µL and a platelet count > 75,000/µL before proceeding with therapy.

High Dose Cytarabine (HD ARAC): IV over 3 hours

Days: 1, 2 and 8, 9

Dose: 3,000 mg/m²/dose, every 12 hours (i.e., 6,000 mg/m²/day, divided BID), or

100 mg/kg/dose, every 12 hours (i.e., 200 mg/kg/day, divided BID) if BSA < 0.6 m².

Suggested premedications and supportive care: Administer steroid eye drops (0.1% dexamethasone or 1% prednisolone ophthalmic solution), 2 drops to each eye every 6 hours, beginning immediately before the first dose and continuing for 24 hours after the last dose. If patient does not tolerate steroid eye drops, may administer artificial tears on an every 2-4 hour schedule. Patients in whom serum creatinine is > 2 mg/dL or > 2 x normal for age, must have a CrCl performed (Days 1 and 8) and doses of cytarabine adjusted as outlined.

Erwinia L-asparaginase (Erwinaze): IM (may be given IV over 1 hour)

Days: 2, 9 (one dose per day, 2 doses total for the entire course)

Dose: 25,000 IU/m² (830 IU/kg/dose if BSA < 0.6 m²)

Note: Erwinia asparaginase should be given 6 hours after the start of cytarabine doses 4 and 8. If Erwinia asparaginase is not available, pegaspargase should not be given. Rather, asparaginase should be omitted.

Sorafenib (SORAF): PO

Days: 11 through 28.

Dose: 200 mg/m²/dose daily, rounded to accommodate tablet size. The maximum dose will be 400 mg. Dose will be administered per dosing nomogram in Appendix I.

Note: Sorafenib tablets should be taken at least 1 hour before or 2 hours after food. Tablets should be taken with clear liquids (approximately 2 to 4 ounces for children < 12 years and 4 to 8 ounces for ≥ 12 years). If taken with food, sorafenib should be taken with a moderate to low fat meal. Tablets should not be crushed and should be swallowed whole. However, sorafenib tablets can be dispersed in water to facilitate the administration to subjects that cannot swallow tablets.

6.0 DOSE MODIFICATION FOR TOXICITIES

Common Terminology Criteria for Adverse Events (CTCAE)

The descriptions and grading scales found in the revised NCI Common Terminology Criteria for Adverse Events (CTCAE) version 5.0 will be utilized for AE reporting. All appropriate treatment areas should have access to a copy of the CTCAE version 5.0. A copy of the CTCAE version 5.0 can be downloaded from the CTEP website (<http://ctep.cancer.gov>).

6.1 Allergy to Asparaginase

6.1.1 Local Reactions (Inflammation at Injection Site, Swelling):

Continue asparaginase (*Erwinia*) administration in the presence of Grade 1 allergic reaction (transient flushing or rash; drug fever < 38°C).

Premedication with antihistamines to decrease the risk of overt allergy symptoms is strongly discouraged since antihistamine use may mask the appearance of systemic allergy. Systemic allergy is associated with the presence of asparaginase neutralizing antibodies, which render asparaginase therapy ineffective.

6.1.2 Anaphylaxis/Systemic Allergic Reactions:

Discontinue asparaginase (*Erwinia*) if the patient develops a systemic allergic reaction (urticaria, wheezing, laryngospasm, hypotension, etc.). Should an allergy be diagnosed after the first dose given on Day 2 during Intensification II (for high risk patients), then the dose due on Day 9 should not be administered.

6.2 Allergy to Etoposide

Etoposide allergic reactions may be managed with pre-medications such as diphenhydramine 1 mg/kg IV (maximum dose 50 mg) or an equivalent H-1 receptor antagonist, ranitidine 1 mg/kg IV (maximum dose 50 mg) or an equivalent H-2 receptor antagonist, hydrocortisone 1 - 4 mg/kg IV, and by slowing the rate of the infusion OR etoposide phosphate may be substituted in the same dose and at the same rate. Premedication for etoposide phosphate is recommended.

6.3 Cardiac Toxicity

6.3.1 Left Ventricular Systolic Dysfunction:

Daunorubicin, mitoxantrone, and sorafenib will be held if there is significant evidence of cardiac disease by echocardiogram (shortening fraction < 28% or EF < 55%). Cardiac examination with echocardiogram is required prior to the start of all chemotherapy courses, at the end of protocol therapy, and in follow up. Echocardiogram and cardiac biomarker evaluation (i.e. troponin) are also strongly recommended, particularly in clinical scenarios with potential or suspected cardiac dysfunction.

6.3.2 Daunorubicin and Mitoxantrone:

Do not re-start anthracyclines if held for left ventricular shortening dysfunction that is not associated with a microbiologically proven bacteremia or sepsis. If the left ventricular shortening dysfunction occurred in the setting of microbiologically proven bacteremia or sepsis, then anthracyclines may be reinstated at the treating clinician's discretion once the shortening fraction has returned to $\geq 28\%$ or $EF \geq 55\%$.

6.3.3 Sorafenib in Combination with Chemotherapy:

Sorafenib should be held for a shortening fraction of $< 28\%$ or $EF < 55\%$ regardless of attribution. Sorafenib should be restarted at a reduced dose (100 mg/m^2) when the shortening fraction has returned to $\geq 28\%$ or $EF \geq 55\%$. If SF decreases below

28% or EF decreases below 55% on 100 mg/m², then sorafenib should be discontinued permanently. Sorafenib dose may not be re-escalated in combination with chemotherapy.

6.3.4 Hypertension:

The table below will be used to manage hypertension possibly, probably or definitely related to sorafenib. Management of hypertension not related to sorafenib is at the treating clinician's discretion. Should initiation of anti-hypertensive (anti-HTN) therapy be required, single agent therapy (such as amlodipine or nifedipine) should be started. For patients greater than age 18, rely on CTCAE v.5.0 grading of hypertension for consideration of dose adjustment.

GRADE	MANAGEMENT
For grade 1	No anti-HTN therapy, no change in sorafenib dose
For grade 2	Initiate monotherapy with anti-HTN medication, no change in sorafenib dose
For grade 3	Add additional agent for anti-HTN therapy, hold sorafenib dose. Restart if blood pressure comes back in range for age, gender then dose reduce sorafenib to 100 mg/m ² /day
For grade 4	Permanently discontinue sorafenib

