2.3 Rationale for use of Dexrazoxane with anthracyclines

Cumulative incidence of heart failure and other cardiac events in patients with acute leukemias ranges from 4-10% at 10-20 years from diagnosis^{28,29}. While late cardiotoxicity has been

described well following anthracycline exposure above 250-300 mg/m² doxorubicin equivalents, early cardiotoxicity is a growing concern³⁰. Evaluation of cardiotoxicity (defined as grade 2 or higher left ventricular dysfunction per CTCAE version 5.0) on COG AAML0531 showed an incidence of 12% over a five-year follow-up period with most of the events occurring while on protocol therapy. Black, older patients (>1 year age) and concurrent infection were risk factors associated with worse cardiac outcomes³⁰.

Dexrazoxane is a bis-dioxopiperazine compound that was introduced in the early 1990's and has been shown to reduce cardiotoxicity related to anthracyclines initially in animal models and later in clinical studies^{31,32}. While the exact mechanism is poorly understood, it is believed that anthracyclines form complexes with heavy metals specifically iron and generate free radicals that cause cardiac damage³³. Dexrazoxane binds to iron and prevents the generation of free radicals thereby reducing cardiotoxicity. Dexrazoxane has been used successfully in combination with various chemotherapy regimens with acceptable toxicity and enhanced cardio-protection^{34,35}. While there was concern regarding development of secondary malignancies with exposure to dexrazoxane, recent literature has not supported this side-effect³⁶. In this study, all patients will receive dexrazoxane in anthracycline-containing treatment courses. We will closely monitor for infection, cardiac, hepatic and hematologic toxicities as well as development of secondary malignancies. In addition, we will obtain more precise measurements of cardiac function using echocardiogram at the end of each course (Section 8.0) as noted in Table 4.

Table 4: Variables of cardiac function to be determined using echocardiography

Left ventricle (LV) remodeling	LV thickness to dimension ratio
LV myocardial deformation	Strain and Strain rate imaging
LV systolic function	LV Ejection Fraction using biplane Simpson method LV Shortening fraction using 2D and M-mode Mitral and septal S'

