2.4 Use of FLT3-ITD inhibitors in AML

Presence of activating mutations in the FLT3 gene occurs in approximately 15% of pediatric patients with de-novo AML³⁷. Patients with FLT-ITD mutations with a high allelic ratio (HAR>0.4) have an extremely poor progression-free survival of 16% compared to those with lower allelic ratios³⁸ and are therefore categorized in the high risk group post induction. Further analysis of FLT3-ITD mutations has suggested an AR>0.1 to be associated with a poor outcome as well (COG, internal communication). Several FLT3-ITD inhibitors are currently in clinical trials and COG AAML1031 tested the inclusion of one such inhibitor, sorafenib, with the regular chemotherapy backbone in FLT3-ITD positive AML in a non-randomized fashion. The results of this combination are currently under review; however the combination is believed to be safe

(COG, internal communication). In this study, we will use sorafenib as the FLT3 inhibitor of choice in patients with FLT3-ITD HAR (>0.1) AML.

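### Section 6.3.3 restarts sorafenib when shortening fraction or ejection fraction recovers but holds it when either is low, so a patient with only one recovered meets both rules

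*Combined protocol and SAP*

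**What the plan says.** All of the rules are in section 6.3 (Cardiac Toxicity) of the combined protocol and SAP.

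- **General hold, 6.3.1.** Daunorubicin, mitoxantrone and sorafenib will be "held if there is significant evidence of cardiac disease by echocardiogram (shortening fraction < 28% or EF < 55"%).
- **Echo schedule, 6.3.1.** "Cardiac examination with echocardiogram is required prior to the start of all chemotherapy courses", and again at the end of therapy and in follow-up. Further echocardiograms and troponin are strongly recommended when dysfunction is suspected.
- **Sorafenib hold, 6.3.3.** "Sorafenib should be held for a shortening fraction of" less than 28%, or an EF under 55%, whatever the cause.
- **Sorafenib restart, 6.3.3.** "Sorafenib should be restarted at a reduced dose", 100 mg/m², when SF has come back to 28% or more *or* EF to 55% or more.
- **Sorafenib permanent stop, 6.3.3.** If SF or EF decreases below its threshold on 100 mg/m², "then sorafenib should be discontinued permanently". Re-escalation with chemotherapy is not allowed.
- **Anthracycline restart, 6.3.2.** There is no restart unless the dysfunction came with proven infection. "If the left ventricular shortening dysfunction occurred in the setting of microbiologically proven bacteremia or sepsis, then anthracyclines may be reinstated" at the clinician's discretion, on the same SF *or* EF criterion.

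**The concern.** A restart criterion should describe the patients who no longer meet the hold criterion. The opposite of *SF low or EF low* is *SF in range and EF in range*. Section 6.3.3 has *or* on both sides, so some patients satisfy both.

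The clear case is a patient in whom both measures fell and one recovered. With SF 30% and EF 48%, a fallen measure has returned to range, so the text says to restart. EF is still under 55%, so the text also says to hold. Discordant readings are possible in practice, because Table 4 in section 2.3 plans both EF (biplane Simpson) and SF (2D and M-mode).

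Read literally, the rule directs sorafenib in a child who still meets the trial's own hold criterion. At EF 48% that child also meets the secondary cardiotoxicity endpoint of EF below 50%. The agent information for sorafenib (section 9.6) lists left ventricular systolic dysfunction and heart failure among its rare but serious events, and sparing the heart is a stated aim of the trial.

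**Working it through.** **1. Logic.** The plan states no figure to reproduce here. The check applies each rule to one value on either side of each threshold.

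| SF | EF | Hold (SF <28 or EF <55) | Restart as written (SF ≥28 or EF ≥55) | Restart with *and* |
|---|---|---|---|---|
| 27% | 54% | yes | no | no |
| 27% | 55% | yes | yes | no |
| 28% | 54% | yes | yes | no |
| 28% | 55% | no | yes | yes |

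As written, hold applies in 3 of the 4 states, restart in 3, and both in 2. With *and*, hold applies in 3, restart in 1, both in 0 and neither in 0.

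The two overlapping states do not always conflict. If only one measure ever fell, *returned* can be read as that measure recovering. The clear conflict is the path from both low to one recovered.

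**2. Consequence for the permanent stop.** Suppose sorafenib is restarted at SF 30%, EF 48%. If *decreases below* means crossing the threshold on treatment, EF cannot trigger the stop, because it is already below. If it means being below, the stop is met at the moment of restart. The SF part of the sentence still works.

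**3. How many patients.** Inputs:

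- Planned enrolment is 30 (section 3.0).
- "Presence of activating mutations in the FLT3 gene occurs in approximately 15% of pediatric patients" (section 2.4).
- Grade 2 or higher left ventricular dysfunction on AAML0531 "showed an incidence of 12% over a five-year follow-up period with most of the events occurring while on protocol therapy" (section 2.3).

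Expected sorafenib patients: 30 × 0.15 = 4.5. This is an expectation, not a maximum; the central 95% binomial range is 1 to 9. The 15% covers activating FLT3 mutations generally, while section 2.4 limits sorafenib to FLT3-ITD with allelic ratio above 0.1.

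Expected sorafenib patients with any such dysfunction: 30 × 0.15 × 0.12 = 0.54. The chance of at least one is 1 − (1 − 0.018)^30 = 42%, where 0.018 = 0.15 × 0.12.

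The documents do not give the share of these with both measures low and only one recovered. Assuming 10% to 50%:

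- Expected affected: 0.54 × 0.10 = 0.05 to 0.54 × 0.50 = 0.27.
- Chance of at least one: 1 − (1 − 0.0018)^30 = 5% to 1 − (1 − 0.009)^30 = 24%.

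The hold threshold (EF <55%) is looser than the grade 2 threshold (EF <50%), so holds may be more frequent than 12%. If the rate were doubled to 24%, the expected range would be 0.11 to 0.54.

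**4. Exposure per affected patient.** The longest sorafenib blocks are days 7–34 (Induction II) and days 6–33 (Intensification I), 28 daily doses each. The ceiling before the next required echo is 28 × 100 = 2,800 mg/m². It assumes no extra echo in between.

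**The case against.** The strongest reply is that the hazardous reading is the less likely one. Section 6.3.1 says the drugs *will* be held, which is firmer than *should* be restarted, and 6.3.3 repeats the hold whatever the cause. *Returned* most naturally refers to every measure that fell. The restart is at half dose without re-escalation, an extra echo is strongly recommended for just such a patient, and section 10.2 lets the physician stop protocol therapy in the patient's interest.

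This lowers the risk but does not settle the text. Within 6.3.3 the hold and the restart carry the same verb, and no sentence says that both measures must recover or which prevails.

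Three stronger readings are tempting, and the documents do not support them.

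- **That anthracyclines are also directed to restart against a hold.** Section 6.3.2 only permits reinstatement, at discretion and after microbiologically proven bacteremia or sepsis. A clinician who keeps holding complies with both sections. The criterion is looser than the 6.3.1 hold, but nothing in it directs a dose.
- **That the permanent-stop sentence is a second defect.** It becomes unclear only for a patient already restarted with one measure low, so it follows from the same *or*.
- **That a reliable count of affected patients can be given.** The share on the conflict path is assumed. For anthracyclines a count is weaker still. The 12% spans five years, while anthracyclines are given only in the two induction courses. Multiplying by an infection rate would also assume independence, yet section 2.3 names concurrent infection as a cardiac risk factor. No anthracycline count is offered here.

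**Conclusion.** Wrong as written; a minor safety correction. For a patient in whom SF and EF both fell and one recovered, 6.3.3 requires the hold and also says to restart sorafenib at 100 mg/m². The permanent stop is then unclear for that patient. Section 6.3.2 shares the loose wording but creates no directive conflict.

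Probably no more than one of the 30 patients would be affected, and quite possibly none. That rests on 0.54 expected sorafenib patients with any dysfunction, taking the FLT3 and AAML0531 rates from the protocol and assuming they multiply. The unknown share can only reduce that figure; a hold rate above 12% would raise it. The logical finding depends on none of these numbers.

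A reader might infer that the trial's results are at risk. They are not: the sample size, the event-free survival analysis and the analysis sets do not depend on this rule.

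**What to change.** In the restart sentence of 6.3.3, replace *or* with *and*: sorafenib is restarted at 100 mg/m² once SF is at least 28% and EF is at least 55%, with any measure that was below threshold at the hold re-measured and back in range. Make the same change in 6.3.2 for consistency, leaving its discretion and infection conditions as they are.

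No echo result then meets both rules. Every patient restarted on sorafenib begins in range, so the permanent-stop sentence works without rewording.

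The cost is one word and one clause in each of two sentences, with no change to design, sample size or analysis. The small downside is that a few patients may restart later, or stay on hold while one measure remains low.
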